13. PUBLICATIONS

The Steering Committee will develop a detailed publications policy. Copies will be distributed to all Clinical Site PIs and the NIDCD Project Scientist. The goals of this policy are to (1) assure and expedite orderly and timely presentation to the scientific community of all pertinent data resulting from the AVERT study; (2) have accurate and scientifically sound presentations and papers; (3) assure that all investigators, including those of junior faculty rank and other professionals have the opportunity to participate and be recognized in study-wide presentations and the preparation of AVERT papers; (4) assure that press releases, interviews, presentations, and publications are accurate and objective, and do not compromise the collaborative trial and the acceptance of its results; and (5) establish procedures for review and approval of ancillary study applications.

1 TRIAL SUMMARY

1.1 Introduction

This study seeks to improve clinical care for peripheral and central vestibular disorders by translating recent advances in vestibular physiology to clinical practice. The **AVERT** Trial (Acute Video-oculography for Vertigo in Emergency Rooms for Rapid Triage) is a multicenter, randomized, phase 2 clinical trial of video-oculography (VOG)-guided vs. standard care to improve diagnosis and initial management for patients with a chief symptom of vertigo or dizziness suspected to be of vestibular cause. We will recruit 226 adults from five EDs.

[figure not shown]
1.2 Objectives

- 1.2.1 To measure the impact of VRT on diagnosis and initial management in ED vertigo/dizziness.
- 1.2.2 To measure the impact of VRT on initial diagnostic work-up costs in ED vertigo/dizziness.
- 1.2.3 To compare short-term clinical outcomes in those correctly diagnosed vs. those misdiagnosed.
- 1.2.4 To develop a training library of educational materials related to eye-movement interpretation.
- 1.2.5 To measure the diagnostic accuracy of expert interpretation of VOG in ED vertigo/dizziness.

1.3 Study design

Randomized controlled trial (individual patient randomization), parallel design (1:1) (Figure 1).

Patients screened but not eligible for randomization will be enrolled in an observational arm that undergoes limited follow-up to ascertain for clinical outcomes, particularly stroke events.

Trial Arm 1 VRT (intervention arm): VOG-based logic rules determine rapid triage pathway.

Trial Arm 2 Standard Care (control arm): usual ED care plus VOG exam, no VOG report generated.

Observational arm: ED MRI VOG and six-month follow-up.

1.4 Recruitment

For the main clinical trial, we expect to enroll (randomize) approximately 226 participants recruited from the ED across the five sites, approximately 75 per site (the Johns Hopkins and University of Michigan will each recruit a total of 75 subjects from all of their institutional ED sites combined).

2. STATISTICAL ANALYSIS PLAN

2.1 General Design Issues

Main trial design: Randomized controlled trial (individual patient randomization), parallel design (1:1). Results will be used for primary outcome analyses related to diagnosis accuracy at the ED index visit.

Secondary cohort design: Cohorts will be followed for adverse events and functional outcomes (1wk, 30d). Estimates will be used for phase 3 trial planning for the impact of diagnosis accuracy on clinical events and outcomes. The 6-month follow-up time point (if available) will not be part of the primary trial outcomes.

Observational arm: Patients with vestibular symptoms but no signs or who are not randomized for other reasons (see Inclusion and Exclusion Criteria) will be eligible for a parallel track observational sub-study with limited phone follow-up.

Diagnosis adjudication: Prior to adjudication, index VOG results will be interpreted by two independent vestibular experts masked to allocation. They will be given only patient demographic information, a structured summary of dizziness-related history of the present illness, and bedside hearing test results. Using this information, and masked to all other index visit clinical findings, ED physician diagnoses, any neuroimaging, and all follow-up data, they will render an ED index visit diagnosis (“Index VOG Diagnosis”). Prior to adjudication, MRIs will be interpreted by two independent neuro-radiologists masked to allocation and all clinical findings other than demographic information. They will render an index visit diagnosis (“Index Radiology Diagnosis”). A 5-member multidisciplinary panel with ED physician, otolaryngologist, vestibular neurologist, stroke neurologist, and neuro-radiologist will adjudicate diagnoses. The panel will be masked at all times to trial allocation (VRT vs. standard care). Diagnoses will be classified into 1 of 6 diagnostic categories likely to affect ideal ED management and rated as probable or definite based on neuroimaging results and standard clinical criteria. Diagnoses will be rendered in two stages – first based on VOG and all clinical data (including eye videos) from the ED index visit alone, without follow-up data (“Adjudicated Index Diagnosis”); then again after all 1-week testing and 30-day follow-up data are revealed electronically (“Adjudicated Final Diagnosis”). All differences will be resolved by discussion or majority vote.

Outcome assessment: The ED diagnosis will have been elicited from ED providers by study personnel as a forced choice diagnosis. For the primary outcome, a correct “ED SOC Diagnosis” requires that the “Adjudicated Final Diagnosis” is the same diagnostic category. The VRT diagnosis will be assigned automatically by the online algorithm in real-time.

2.2 Outcomes

2.2.1 Aim 1 (Trial Outcome): Measure the impact of VRT on diagnosis and initial management

Hypothesis 1: The VRT pathway will yield more correct diagnoses by the end of the ED index visit than the standard care (ED provider-determined) pathway.

Primary outcome 1: Six-Category Diagnosis Accuracy (all, VRT vs. SOC). Total proportion of correct diagnoses made by VRT vs. SOC among subjects with 30-day adjudicated final diagnoses (the gold standard) categorized in one of six possible diagnosis categories (3 peripheral, 1 central, 1 medical/other, 1 non-diagnosis).

Statistical Analysis Plan 1:

Primary analysis 1: A generalized linear model with a log link will be used for comparing the true positive rates (TPRs) of VRT and SOC. Without additional covariates, the model-based score test is equivalent to a Pearson Chi-square test for unpaired data. The regression model will assess the influence of demographic and key clinical variables as exploratory subgroups. Generalized estimating equation (GEE)¹⁶¹ method will be used to account for clustering effects by hospital site or provider. VOG non-completers are excluded pre-randomization (randomization occurs post-VOG for all patients).

Specifically, define $D_i = 1$ if the 30-day adjudicated final diagnosis for the i th subject is categorized in one of six possible diagnosis categories (3 peripheral, 1 central, 1 medical/other, 1 non-diagnosis). Define a test variable as

$$X_{Test} = \begin{cases} 1 & \text{for VRT} \\ 0 & \text{for SOC} \end{cases}$$

Define $Y_i(\text{VRT}) = 1$ if the index VRT diagnosis for the i th subject is the same as his/her 30-day adjudicated final diagnosis and $Y_i(\text{VRT}) = 0$ otherwise. Similarly, define $Y_i(\text{SOC}) = 1$ if the ED SOC Diagnosis for the i th subject is the same as his/her 30-day adjudicated final diagnosis and $Y_i(\text{SOC}) = 0$ otherwise.

The TPR, over the total proportion of correct diagnoses, is defined as follows

$$TPR(X_{Test}) = P[Y_i(X_{Test}) = 1 | D_i = 1], \quad X_{Test} = 0, 1.$$

Define the regression model as

$$\log TPR(X_{Test}) = \alpha_0 + \alpha_1 X_{Test} + \overline{\alpha_i} \cdot \overline{X_i}$$

where $\overline{X_i}$ is a vector of additional subgroup variables or other covariates to be explored for assessing the influence of demographic and key clinical variables described in the secondary analysis.

Secondary analysis 1: For each of the six possible diagnosis categories (3 peripheral, 1 central, 1 medical/other, 1 non-diagnosis), define the gold standard =1 if the 30-day adjudicated final diagnosis is the corresponding category and 0 otherwise. Define test positive respectively for “Index VRT Diagnosis” and “ED SOC Diagnosis” if the diagnosis is the corresponding category and 0 otherwise. Estimate sensitivity, specificity, predictive values and likelihood ratios accordingly for “Index VRT Diagnosis” and “ED SOC Diagnosis”. Between-arm comparisons will be performed by the generalized linear model with a log link as described in primary analysis 1a.

Tertiary analysis 1: Subgroups and covariates:

The regression model is

$$\log TPR(X_{Test}) = \alpha_0 + \alpha_1 X_{Test} + \overline{\alpha_l} \cdot \overline{X_l}$$

where $\overline{X_l}$ is a vector of additional subgroup variables or other covariates to be explored for assessing the influence of demographic and key clinical variables described below.

1) Potential Subgroups:

- a. AVS-Only Group: using only patients with acute (continuous) vestibular syndrome >24hr.
- b. Younger-Patient Group: using only patients 49 years of age or younger (i.e., 18-49).
- c. Women-Minority Group: using only patients self-identifying as female, minority, or Hispanic.
- d. NIHSS 0 Group: using only patients with an NIH stroke scale score of zero at ED index visit.
- e. Stands-Independently Group: using only patients who stand without assistance or support.
- f. Normal Hearing Group: excluding any patient with hearing loss (new or old).
- g. Non-AICA Group: excluding any patient with an AICA-territory stroke diagnosis.
- h. Pre-Treatment Group: using only patients with results obtained prior to anti-vertigo meds.
- i. VRT Definite-Only Group: using only “definite” VRT diagnoses (excluding VRT-E cases).
- j. Specific ED-Only Diagnosis Group: using only “definite” ED diagnoses (excluding ED O2).
- k. Neuro-otologic Diagnosis Group: using only patients with peripheral or central diagnoses.

2) Potential Covariates:

- l. Site: JH vs. UI vs. UM.
- m. Age (ordinal): 18-49, 50-59; 60+ years.
- n. Age (continuous): for each year.
- o. Sex: female vs. male.
- p. Race/Ethnicity: minority vs. non-Hispanic white.
- q. Symptom Onset (ordinal): 0-24, 25-48, 49-72, >72 hours.
- r. Symptom Onset (continuous): time from symptom-onset for each hour.
- s. Symptom Type: vertigo vs. dizziness vs. unsteadiness.
- t. Symptom Severity: VSS-SF score.
- u. Vestibular Syndrome: episodic positional vs. episodic spontaneous vs. acute continuous.
- v. Hearing Loss: new hearing loss vs. no new hearing loss.
- w. Vascular Risk Severity (continuous): ABCD2 (0-7).
- x. Neurologic Severity (continuous): NIHSS (0-42).
- y. Ataxia Severity (continuous): SARA score (0-40).
- z. Stroke size (continuous): greatest dimension in millimeters.
 - aa. Stroke location: none, hemispheric-only, posterior fossa (with or without hemispheric).
 - bb. Confounded: unconfounded vs. potentially confounded (medications or illnesses).
 - cc. Comorbidities (continuous): Charlson Comorbidity Index (0-56).

Secondary outcomes 1.1-1.2: Diagnosis accuracy for different category groupings and comparisons; the following accuracy comparisons are considered:

1. Expert VOG Six-Category Diagnosis Accuracy (SOC arm, expert VOG vs. ED SOC)

Total diagnosis accuracy adjudicated expert VOG diagnosis vs. ED SOC using 30-day adjudicated final diagnoses categorized in one of six diagnosis categories (3 peripheral, 1 central, 1 medical/other, 1 non-diagnosis). We will use “Index Expert VOG Diagnosis” and “ED SOC Diagnosis” within the SOC arm based on ED index visit and 30-day follow-up clinical assessments. This within-subject comparison reflects the current potential accuracy of expert VOG-based tele-diagnosis and the targeted maximum diagnostic accuracy performance (i.e., expert level) of future automated algorithms.

2. Stroke-No Stroke Diagnosis Accuracy (all, VRT vs. SOC)

Total diagnosis accuracy VRT vs. SOC using 30-day adjudicated final diagnoses categorized as stroke vs. no stroke (including peripheral vestibular, medical, psychiatric, or other central neurologic causes such as multiple sclerosis, traumatic brain injury, epilepsy, or anticonvulsant toxicity).

Statistical Analysis Plan Secondary Outcomes 1.1-1.2: A generalized linear model with a log link will be used for comparing the true positive rates (TPRs) of VRT and SOC. Without additional covariates, the model-based score test is equivalent to a Pearson Chi-square test for unpaired data. The regression model will assess the influence of demographic and key clinical variables as exploratory subgroups. Generalized estimating equation (GEE)¹⁶¹ method will be used to account for clustering effects by hospital site or provider.

2.2.2 Aim 2 (Trial Outcome): Measure the impact of VRT on initial diagnostic work-up costs

Hypothesis 2: The VRT pathway is cost saving relative to current ED practice in diagnostic assessments.

Primary outcome 2: Total dollar costs of VRT as compared to SOC for diagnostic tests and consultations obtained during the ED index visit and hospital admission (for those admitted at the index visit). The cost for VRT arm does not include the costs of protocol safety MRIs or any tests not specified by the pathway but ordered for clinical purposes by ED providers. It does include tests ordered as part of the VRT pathway by consultants or ED providers in the “equivocal” pathway. Total costs will be calculated by multiplying fixed cost estimates (most recent year available average Medicare reimbursement in US dollars) by utilization rates for each ED index visit service tracked.

Statistical Analysis Plan 2: Analyses will include two-sample comparisons of mean and median costs. Mean of total cost between two study-arms will be compared by modified t-test with unequal variances. Median total cost between two study-arms will be compared by Wilcoxon-Mann-Whitney tests.¹⁶²

2.2.3 Aim 3 (Observational Outcome): Compare clinical outcomes for correct vs. incorrect diagnoses

Hypothesis 3: ED patients with vertigo or dizziness who receive standard care will have better outcomes if correctly diagnosed than if misdiagnosed (*this is an observational outcome in the standard-care arm*).

Primary Outcome 3: Proportion with short-term prespecified medical events of interest (PMEIs) occurring between the time of ED index visit disposition and 1-week research follow-up visit among those with correct vs. incorrect ED SOC diagnosis. “Correct” vs. “incorrect” diagnoses are categorized in one of six possible diagnosis categories (3 peripheral, 1 central, 1 medical/other, 1 non-diagnosis). PMEIs will include ED revisits, falls, vascular events (including stroke), and test or treatment complications.

Statistical Analysis Plan 3: A multivariable logistic regression will be used to estimate the odds of an PMEI (correct diagnosis vs. misdiagnosed) adjusting for demographic and clinical variables.

Specifically, define $S_i = 1$ if the i th subject experience PMEIs between the time of ED index visit disposition and 1-week research follow-up visit. Following notation used in Aim 1, define the logistic model as

$$\text{logit } P(S_i = 1 | X_{Test} = 0) = \beta_0 + \beta_1 Y_i(0) + \overline{\beta_2} \cdot \overline{Z_i}$$

where $Y_i(0)$ is the variable indicating correct or incorrect diagnoses in SOC arm as defined in Aim 1, $\overline{Z_i}$ are additional subgroups variables or other covariates listed in Aim 1.

In addition, standard time-to-event analyses (Kaplan-Meier,¹⁶³ Cox regression¹⁶⁴) will be used to estimate relative hazard ratios, adjusting for demographic and clinical variables listed in Aim 1.

Exploratory Outcomes:

1. Preventable Six-Category Diagnosis Error (all, VRT vs. SOC)

Total diagnosis inaccuracy (error) VRT vs. SOC using adjudicated index diagnoses categorized in one of six diagnosis categories (3 peripheral, 1 central, 1 medical/other, 1 non-diagnosis). Adjudicated index diagnoses will be determined using only ED index visit data that “would have been” available clinically (i.e., excluding safety MRI, index hospital admission data, and all follow-up data).

2. VRT vs. MRI Stroke-No Stroke Diagnosis Accuracy (VRT arm only, VRT vs. MRI)

Total diagnosis accuracy VRT vs. index imaging using 30-day adjudicated final diagnoses categorized as stroke vs. no stroke (posterior fossa mass lesion, encephalitis, etc.). The VRT arm is chosen here because all VRT arm patients will undergo MRI at the index visit (protocol, clinical, or safety), eliminating diagnostic ascertainment bias that may be present in the SOC arm.

3. Algorithm-Only VRT Six-Category Diagnosis Accuracy (all, initial VRT output vs. SOC)

Total diagnosis accuracy “as computed in real time,” algorithm-only VRT diagnosis vs. SOC using 30-day adjudicated final diagnoses categorized in one of six diagnosis categories (3 peripheral, 1 central, 1 medical/other, 1 non-diagnosis). We will use “Index VRT Diagnosis” and “ED SOC

Diagnosis" compared to the "Adjudicated Final Diagnosis" based on ED index visit and 30-day follow-up clinical assessments. This outcome measure reflects the weighted average diagnostic accuracy of the various versions of the automated algorithm as it would have been absent human double-check during the course of the trial.

4. Optimized Six-Category Within-Subject Accuracy (SOC arm only, optimized VRT vs. SOC)

Total diagnosis accuracy optimized VRT vs. SOC using 30-day adjudicated final diagnoses categorized in one of six diagnosis categories (3 peripheral, 1 central, 1 medical/other, 1 non-diagnosis). We will use "Optimized VRT Diagnosis" and "ED SOC Diagnosis" compared to the "Adjudicated Final Diagnosis" based on ED index visit and 30-day follow-up clinical assessments. Optimized VRT diagnoses will be run using the final (end-of-trial) version of the VRT algorithm. Only SOC-arm subjects are used for this outcome, as VRT patient results will have been used to optimize the algorithm during the trial. VRT diagnoses in the SOC arm (algorithm not run during the trial), will be assigned based on the final, optimized algorithm; for this purpose, the ED SOC diagnosis will be assigned as the VRT diagnosis for algorithm results in the VRT-E group. This outcome measure reflects the estimated diagnostic accuracy of the end-of-trial automated algorithm.

5. Central-Peripheral Diagnosis Accuracy (all, VRT vs. SOC)

Total diagnosis accuracy VRT vs. SOC using 30-day adjudicated final diagnoses categorized as central (stroke, posterior fossa mass lesion, encephalitis, demyelinating disease, etc.) vs. non-central (includes peripheral vestibular, medical, psychiatric, non-diagnoses, etc.).

6. Central Discharge Proportion (central subgroup only, VRT vs. SOC)

Total discharge proportion of central causes VRT vs. SOC. Central causes determined based on 30-day adjudicated final diagnosis.

7. Peripheral Admission Proportion (peripheral subgroup only, VRT vs. SOC)

Total admission proportion of peripheral causes VRT vs. SOC. Peripheral causes determined based on 30-day adjudicated final diagnosis.

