4.3.6 Randomization: Patients who meet all of the inclusion and exclusion criteria using the above screening procedures and who provide consent will be randomized. AVERT randomization will initially assign each patient to a block size of 2 or 4, with a 50-50 probability; all site personnel will be masked to this block assignment. Then, when the patient is determined to be eligible for the study, the patient will be randomized using VISION’s randomization framework, stratified by site and block size, so that all patients assigned to size “2” are randomized in blocks of 2 and all patients assigned to “4” are randomized in blocks of 4 at each site. In this way, it would be difficult for the site personnel to predict the next assignment, as they will not know which patients are in which block.

VISION’s just-in-time randomization framework generates each random treatment at the moment a patient is randomized, instead of reading from a pre-computed table of treatments. This automatically compensates for

imbalances caused if a previously-randomized patient drops out of the study or accidentally receives the wrong treatment. When a random choice is made, VISION uses a cryptographically-strong SecureRandom random number generator. The SecureRandom algorithm computes the SHA-1 hash over a true-random seed value concatenated with a 64-bit counter, which is incremented by 1 for each operation. From the 160-bit SHA-1 output, only 64 bits are used. As a result, there is no known computer analysis which is able to predict the next “toss” better than 50% of the time.

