2.3 Sample Size and Accrual

Powering Endpoint: AVERT will be powered to detect a clinically important difference in diagnosis accuracy of 90% vs. 75% (113 per arm). VRT diagnosis is anticipated to be nearly 100% accurate. We have shown that expert eye movement exams have 98.4% (n=187/190) accuracy for differentiating peripheral (vestibular neuritis) from central (stroke) vestibular disorders in acute, continuous vertigo.⁷³ We have now replicated these findings with the VOG device in 21 acute vertigo patients (100% accuracy). The gold standard for BPPV diagnosis is eye movement analysis,^{48,78} often by VOG,^{51,165} so we conservatively estimate that VOG accuracy across all vestibular conditions will be >90%. Diagnosis accuracy of routine ED care varies, estimated at <20% for BPPV and neuritis⁵ and ~70% for stroke, and lower (~50%) if stroke presents with isolated vertigo.^{7,135,136} Best estimates suggest an

Table 3. Comparison of proportions power estimate (alpha 0.05, power 80%)

VOG Care Correct Diagnoses	Standard Care Correct Diagnoses	Per-arm sample (total study sample)
99%	50%	15 (30)
95%	50%	19 (38)
90%	50%	25 (50)
99%	75%	38 (76)
95%	75%	59 (118)
90%	75%	113 (226)

overall correct ED diagnosis rate of about 56% for vestibular patients.¹¹⁴ In EDs with greater access to specialty consultations or frequent MRI neuroimaging, the proportion of correct diagnoses may range higher. We have powered the AVERT Trial for an anticipated worst-case scenario of 90% VOG accuracy and 75% standard care accuracy (Table 3).

Recruitment Capacity: Our 3-site consortium has a total of ~180,000 ED visits per year. Chief symptoms of vertigo/dizziness account for ~3-4% of ED visits.^{15,123} Thus, our 3 sites have ~5,400-7,200 ED dizziness visits per year (~5-7 patients per 24hrs per site). Of these, we estimate ~20-30%²⁰ will meet inclusion criteria (~1-2 patients per 24hrs per site). We will screen during five designated 7-hr shifts weekly, performing VOG on ~3-5 patients per week, enrolling ~2-4 patients per month per site, taking ~3 years to reach 226.

Number of Strokes: With our inclusion criteria, we expect ~10-20% strokes (n=11-23 per arm). This will not yield firm conclusions about VOG stroke accuracy, but should be sufficient for phase 3 trial planning.

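### The primary accuracy comparison has two candidate tests, one a GEE clustered by site or provider; with so few sites that GEE can err either way, so one site-stratified test should be fixed in advance

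*SAP*

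**What the plan says.** SAP 2.2.1, Primary analysis 1, compares the proportion of correct diagnoses between arms with a log-link generalised linear model. It states: "Without additional covariates, the model-based score test is equivalent to a Pearson Chi-square test for unpaired data". Shortly afterwards it adds that a GEE "method will be used to account for clustering effects by hospital site or provider". Protocol 9.2.1 has the same content, and the SAP plan for secondary outcomes 1.1-1.2 repeats it. None of these places gives an order of precedence, a choice between site and provider, a variance estimator, a working correlation, or a correction for few clusters. The model equation contains arm plus exploratory covariates; site is only one of the potential covariates.

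Randomisation is by individual patient, 1:1 (SAP 2.1), and is "stratified by site and block size" (Protocol 4.3.6).

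The number of sites is not consistent:
- SAP 1.1: "We will recruit 226 adults from five EDs"
- SAP 1.4: "approximately 226 participants recruited from the ED across the five sites"
- SAP 2.3: "Our 3-site consortium has a total of ~180,000 ED visits per year"
- SAP tertiary analysis 1, covariate list: "Site: JH vs. UI vs. UM"
- Protocol 1.1 gives four EDs. Protocol section 4 lists six EDs by hospital, and Protocol 4.3.5 brings in a seventh hospital.

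SAP secondary outcome 1 compares expert VOG with the ED diagnosis in the same standard-care patients, but the plan for it describes an unpaired test.

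**The concern.** Two methods are named for one primary comparison, and the second has several forms. If they gave similar answers, the gap would be cosmetic. They do not. A sandwich variance clustered on site estimates the variance from a handful of site-level residuals, and its usual reference distribution assumes many clusters. An analyst following the text could report a p-value and confidence interval from a test that rejects a true null far too often, from one that has lost much of the planned power, or from one that behaves as intended. The choice could be made after the data are seen.

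Site clustering is also the wrong structure here. Both arms are present in every site in near-equal numbers by design, so site is something to stratify on, not a randomised or sampled cluster.

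**Working it through.** **1. Reproduce the plan's sample size.** Inputs (SAP 2.3, Table 3): 90% vs 75%, alpha 0.05, power 80%. Sidedness is not stated; two-sided reproduces the table.

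Uncorrected: n = [1.960·√(2·0.825·0.175) + 0.842·√(0.90·0.10 + 0.75·0.25)]² / 0.15² = (1.053 + 0.443)² / 0.0225 ≈ 99.5, so 100 per arm.

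With continuity correction: (99.5/4)·[1 + √(1 + 4/(99.5·0.15))]² ≈ 112.5, so 113 per arm, as stated. All six rows of Table 3 (15, 19, 25, 38, 59, 113) reproduce with the corrected formula. The calculation contains no clustering or stratification term.

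**2. Candidate tests.** For site k, let n1k and n0k be the patients and ak and bk the correct diagnoses in the VRT and standard-care arms. A and B are the arm totals of correct diagnoses, and p1 and p0 the observed proportions.
- Robust Wald z clustered on site (independence working correlation): ln(p1/p0) / √Σuk², with uk = (ak − n1k·p1)/A − (bk − n0k·p0)/B.
- The same with a small-sample correction: variance times K/(K−1), t reference on K−1 df. With K = 5 the uncorrected z must exceed 2.776·√(5/4) = 3.10 instead of 1.96, which explains the power loss.
- Robust score test: (ΣUk)² / ΣUk², with Uk the site totals of the score under the null. By the Cauchy-Schwarz inequality this cannot exceed K. With three sites it cannot exceed 3, so it never reaches 3.84. With five it reaches 3.84 only if the site contributions are nearly equal.
- Pearson chi-square, and CMH stratified by site.

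**3. Simulation.** 226 patients, 1:1 within site, 40,000 trials per scenario; null 75% vs 75%, alternative 90% vs 75%. Site sizes are assumed: five equal sites, or 75/75/26/25/25 (two institutions at 75, the remaining 76 over three sites). Monte Carlo standard error at 15.6% is √(0.156·0.844/40,000) ≈ 0.2 points.

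| Test, five sites | Type I, equal | Type I, unequal | Power, equal | Power, unequal |
|---|---|---|---|---|
| Site-cluster robust Wald z | 15.6% | 17.2% | not comparable | not comparable |
| Same, K/(K−1) and t on 4 df | 4.9% | 5.8% | 59.5% | 63.6% |
| Site-cluster robust score | 2.2% | 1.8% | 41% | 19% |
| Pearson, both layouts | 4.8-5.4% | | 85.9-86.0% | |
| Site-stratified CMH, both layouts | 4.8-5.3% | | 85.6-85.7% | |
| CMH with continuity correction, both layouts | 3.3-3.7% | | 81.0-81.4% | |

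A separate run with a standard GEE routine, with even more unequal sites (75/75/46/15/15) as the second layout, gave 14.5-14.8% (equal) and 17.9-18.5% for the robust Wald test.

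**4. Sensitivity.** The robust Wald z has about 12-14% type I error with six or seven hospitals, 17-19% with four sites and about 25% with three. An assumed site ICC between 0 and 0.05 changes it little (14.4-15.4% with five equal sites), because the arms are balanced within site. The driver is the number of clusters.

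**5. Site count.** Five sites at about 75 each would be 5 × 75 = 375, not 226; 3 × 75 = 225 fits. The cluster or stratum definition therefore cannot be read off the text.

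**The case against.** The strongest reply is that the SAP names a score test and nowhere mentions a Wald test or a sandwich variance, so the 15-17% belongs to a test of the reviewer's choosing. That stands in part. The nearest GEE extension of the named test, the robust score test, is conservative. A reader might infer that this trial's primary test will have 15-17% type I error. The documents do not support that, because the Pearson-equivalent test is also named and holds its level. What they support is that the test is open and that the site-cluster forms fail in different directions.

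Second, declaring Pearson primary would also close the gap, since its size and power match CMH. That is correct. Stratifying by site is preferred because it follows the randomisation, not because it rescues power. Block size is also a randomisation factor, but it is assigned at random and carries no patient information, so leaving it out is reasonable.

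Third, a reader might infer that dependence among patients diagnosed by the same ED provider or expert reviewer inflates the error by a known amount and calls for clustering on that person. The documents give no provider or reviewer counts and no intraclass correlations. In the VRT arm the SAP assigns the diagnosis by algorithm, and the protocol allows the expert double-check to be withdrawn, so a reviewer cluster may not exist for every patient. No size can be put on this.

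**Conclusion.** The point holds in conditional form and should be fixed. The SAP commits to a GEE alongside a Pearson-equivalent test without saying which decides, on what cluster unit, or with what variance. If a site-cluster GEE is taken as primary with five sites, type I error is about 15-17% (uncorrected Wald z), or power at 90% vs 75% falls to about 59-63% (t correction) or to 41% or 19% (robust score). Pearson and site-stratified CMH hold about 5% with about 86% power. Separately, the unpaired test described for the within-subject secondary outcome does not match that comparison.

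These figures assume that all 226 patients are analysed, the site sizes given above, and no site ICC (0 to 0.05 was checked for type I error). The 113 per arm is correct from its own inputs and is not in dispute. A reader might also infer that the decision to proceed to phase 3 is compromised. Its first limb compares point estimates and is unaffected. The second limb speaks of statistical equivalence and would have to rest on some interval or test, so it is not clearly insulated.

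**What to change.** For the primary outcome and for stroke/no-stroke:
- Declare one primary test: two-sided CMH stratified by site, with the Mantel-Haenszel risk ratio or difference and its 95% CI. The binomial model with site as a fixed effect and model-based standard errors is an acceptable alternative, if it is chosen now.
- Use the site levels in the randomisation system, and reconcile the counts in Protocol 1.1, Protocol section 4, SAP 1.1, SAP 1.4, SAP 2.3 and the site covariate.
- State whether a continuity correction is used. The sample size used one; with it CMH power is about 81%, without it about 86%.
- State that site-cluster GEE variance will not be used for inference.
- Keep GEE by ED provider only as a sensitivity analysis with a named small-sample correction, and say that the CMH result decides if the two differ.

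For SAP secondary outcome 1, use a paired method such as McNemar's test or a GEE clustered on patient.

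The cost is SAP wording and a provider identifier in the analysis file. No patients are added, because power is essentially that of the Pearson test already named (85.6-85.7% against 85.9-86.0%).
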